- Willing to refrain from using any other topical products on the face, systemic retinoids, or steroids, facial peels or other facial laser procedures throughout the duration of the study
- Willing to refrain from any cosmetic procedure including but not limited to facial surgery, dermal fillers, and neuromodulators for the duration of the study
- Willing to use only the facial skin care product regimen provided for the study
- Willing to avoid extended periods of sun exposure and the use of tanning beds during the study
- Willing to have photographs taken of the face to be used de-identified in evaluations, publications, and presentations
- For females: proof that they are not pregnant (urine pregnancy test)
- English-speaker

Exclusion criteria:

- Has any uncontrolled systemic disease (such as autoimmune disorders and

connective tissue disorders such as lupus erythematosus or Sjogren's syndrome
Has any active infection in face
Has history of any skin conditions that could interfere with treatment
Has used self-tanner recently
Is currently participating in another drug research study
Is NOT willing to refrain from using any other topical products such as skin lightening, retinoids, alpha/beta-hydroxyl acids, salicylic acid, vitamins C or D, steroids, or antibiotics on the face or systemic retinoids, steroids, facial peels, neuromodulators, dermal fillers, facial surgery, or other facial laser procedures throughout the duration of the study
For females: is pregnant
Non English-speaker

Individuals will be screened for eligibility via questionnaires that address each of the inclusion and exclusion criteria. Our final study sample will include the subjects who met the inclusion/exclusion criteria and did not voluntarily drop out of the study or develop adverse effects that prohibited them from safely completing the study. We will exclude adults unable to consent, patients under the age of 18, pregnant women, and prisoners.

5) Number of Subjects*

After recruiting our subjects, 14 patients will be randomized into either arm of the study (7 in each arm).

6) Study-Wide Recruitment Methods*

This is a single center study. We will recruit subjects from a clinical database of the practice of [name]. We will use several recruitment methods including invitation via a scripted email providing information describing the study protocol and end-points, scripted invitation telephone calls, and flyers.

7) **Study Timelines***

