	Screening/Baseline Visit 1	Washout period	Visit 2 First Laser treatment (4 weeks +/- 5 days after baseline visit)	Visit 3 Second Laser Treatment (3 weeks +/- 5 days after first laser treatment)	Visit 4 Last day of topical treatment (4 weeks +/- 5 days after second laser treatment)
Procedures					
Informed Consent	X				
Inclusion/Exclusion criteria	X				
Demographic History Questionnaire	X				
Medical History Review	X				
Skincare History Review	X				
Evaluate Fitzpatrick skin type	X				
Evaluate baseline hyperpigmentation	X				
Urine dipstick test	X		X	X	X
Self assessment questionnaire	X				X
Standardized Digital photography	X		X	X	X
Adverse effects review	X		X	X	X
MoPASI evaluation	X		X	X	X
GAIS evaluation	X		X	X	X
Anesthetizing topical application			X	X	X
Protective goggles placed			X	X	
Laser treatment performed			X	X	
Exit Questionnaire					X

Potential participants will receive a thorough history and dermatologic physical exam to determine if patients meet the inclusion/exclusion criteria for being in the study. Urine dipstick tests will be performed on female

patients to confirm they are not pregnant. Consent will be obtained from eligible participants and will be enrolled in the study.

The study will be conducted over a 12 week period. There will be a 4 week washout period prior to laser treatments when the subjects will begin two skin care regimens, which are described below. Then there will be 2 laser treatments separated by 3 weeks. The subjects will continue the topical treatment 1 month after the 2nd laser treatment.

There will be 4 study visits: Baseline Visit 1, First laser treatment Visit 2 (4 weeks +/- 5 days after baseline visit), Second laser treatment Visit 3 (3 weeks +/- 5 days after first laser treatment), and Last day of topical treatment Visit 4 (4 weeks +/- 5 days after second laser treatment). During these visits, photographs of the participants' faces will be taken. Patient questionnaires will be given at baseline and at the end of the study.

Investigators will complete the study 4 months after subjects have completed their participation in the study.

8) Study Endpoints*

The study will reach endpoint for each patient either 1) once they have completed their exit survey after the 2 laser treatments and the topical treatments or 2) if they experience any adverse reactions from treatment and must be pulled from the study.

9) Procedures Involved*

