One month prior to laser treatments (washout period), 14 male and female subjects with moderate hyper pigmentation and photo damage of the face will be randomized to 2 skincare regimens.

The regimens are:

- "Placebo arm" – Basic skin care regimen* (Facial Cleanser, TNS ceramide Treatment Cream (standard post-procedure moisturizer), and Essential Defense Mineral Shield Broad Spectrum SPF35 (all-physical sunscreen))
- "Lytera arm" – Basic skin care regimen + **Lytera 2.0**, which will be added between the Facial Cleanser and TNS Ceramide Treatment Cream

*The basic skin care regimen is a standard regimen used in several skincare product experiments

After cleansing the face, the patients in the Lytera arm will apply one pump of the pigment-correcting serum in a circular motion to the entire face

including the forehead, cheeks, chin, nose, and neck with care to avoid the eyes. The Lytera 2.0 is applied prior to applying moisturizer and sunscreen.

On laser treatment days, patients will come into the office without having applied any topical cream that day. Lidocaine topical may or may not be applied over the face avoiding the eyes (lidocaine use will be at discretion of Principal Investigator), and patients will be given protective goggles to shield the eyes during laser treatment. Next, the laser wand is pressed to the face and passed over the skin in various horizontal and vertical directions. Treatment takes 20 to 30 minutes.

Standardized digital photographs will be taken at baseline and at each subsequent visit using the Canfield VISIA Complexion Analysis (VISIA-CA) camera system at the highest resolution in a consistent position. Pictures will be taken before laser treatments on Visit 2 and Visit 3.

The subjects will complete an exit questionnaire after completion of the study at their last study visit (Visit 4). Through the questionnaire, we will obtain information on subject satisfaction with the study as well as their opinion of how their skin has changed. We hope to use the responses to assess efficacy of our skincare regimen and to improve future related research protocols.

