Lytera 2.0 Pigment Correcting Serum does not contain any known teratogenic ingredients, however, the safety of the product has not been established in women who are pregnant, planning to be pregnant, or breastfeeding. While laser treatment is not recommended during pregnancy, it has not been shown to harbor any risks to the embryo. Patients will need to discuss risks vs benefits with their obstetricians. Subjects who become pregnant during study will not continue participation and will also be instructed to notify their obstetrician about their study participation.

15) Potential Benefits to Subjects*

Benefits to subjects are myriad, as combination topical and laser treatment is intended to moderately improve photo damaged and poor skin tone which can be distressing for patients. Facial cosmetic laser helps prevent and address early signs of aging skin, maintain younger-looking skin, and improve tone, texture and radiance. After even two treatments, patients can expect to have more uniform skin tone, improved texture, more radiant skin, minimized pore size appearance, and skin that looks and feels clear. The skin will continue to improve for several months following treatment.

16) Vulnerable Populations*

We will not be investigating any vulnerable populations. Once again, we will not include pregnant females in the study as skin changes that may be seen in pregnancy may influence the results of the study.

17) Sharing of Results with Subjects*

Results of study will be shared with subjects if they are interested in knowing results. This will be shared over the phone after the data has been analyzed.

18) Setting

Research will be conducted in the Facial Plastic and Reconstructive Surgery Department at the Professional Arts Center at the University of Miami Health System.

19) Resources Available

The principal investigator is a double board certified physician by the American Academy of Otolaryngology and the American Academy of Facial Plastic and Reconstructive Surgery. She has been in practice in Miami for over a decade and is thus very familiar with the population seeking skin care options for photo damage. One of her areas of expertise includes laser treatments for scars and facial rejuvenation. She already uses the laser specific to our study in her practice and is thus quite familiar with it. The secondary investigator is a third year Otolaryngology resident with

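### Section 14 calls the serum's safety unestablished in breastfeeding women and women planning pregnancy, but every eligibility and removal rule acts only on pregnancy; breastfeeding is the main gap

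*Combined protocol and SAP*

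**What the plan says.** Section 14 (Risks to Subjects) first notes that the serum has no ingredient known to cause birth defects. It then says that "the safety of the product has not been established in women who are pregnant, planning to be pregnant, or breastfeeding". It adds that patients should talk to their obstetricians about risks and benefits, and that a subject who becomes pregnant stops taking part.

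The rules on reproductive status are these:

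- Section 4, inclusion: "For females: proof that they are not pregnant (urine pregnancy test"). The exclusion list names current pregnancy, and the closing text says "We will exclude adults unable to consent, patients under the age of 18, pregnant women, and prisoners".
- Section 4, screening: "Individuals will be screened for eligibility via questionnaires that address each of the inclusion and exclusion criteria".
- Section 7: "Urine dipstick tests will be performed on female" patients, scheduled at all four visits.
- Sections 12 and 13: removal if a patient becomes pregnant, or if she later shows any exclusion criterion.
- Section 16: pregnant women are left out because pregnancy may change the skin and so affect the results.
- Section 26: pregnant women are among the populations not enrolled.

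On exposure, Section 5 says "14 patients will be randomized into either arm of the study (7 in each arm"). Section 7 says "There will be a 4 week washout period prior to laser treatments when the subjects will begin two skin care regimens", and Section 9 says "the patients in the Lytera arm will apply one pump of the pigment-correcting serum in a circular motion to the entire face". Sections 9 and 34 withhold topicals on laser days.

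**The concern.** One sentence of the protocol puts three groups on the same footing, and the rules then act on only one of them. Breastfeeding and planned pregnancy appear nowhere else in the document. No exclusion rests on general investigator judgement, so these women would not be caught by another route. The age rule has a lower limit only, and there is no restriction on childbearing potential.

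At stake is exposure of a woman, and possibly a nursing infant, to a product whose safety in her situation the protocol itself calls unestablished. The expected benefit is cosmetic, and Sections 24 and 25 leave the cost of a research injury to the patient or insurer. Section 26 argues that, because the condition is not a grave one, there was no pressing need to include non-English speakers. The same reasoning would apply here, and the plan gives no reason for admitting these two groups.

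**Working it through.** **Rules against groups.** For each group named in Section 14:

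| Group | Eligibility rule | Test | Removal rule |
|---|---|---|---|
| Pregnant | Sections 4, 16, 26 | Dipstick, Visits 1 to 4 | Sections 12, 13, 14 |
| Planning pregnancy | None | None for intent; dipstick detects a resulting pregnancy | Only once pregnant |
| Breastfeeding | None | None | None |

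**Chance of the serum arm.** Section 5 gives 7 of 14, so 7/14 = 0.5 for any enrolled woman.

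**Days on the regimen.** Section 7 spaces the visits at 4, 3 and 4 weeks, each +/- 5 days. The regimen starts with the washout and ends at Visit 4.

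- Visit 1 to Visit 4: 28 + 21 + 28 = 77 days, or 11 weeks. Each window runs from the preceding visit, so they add: 3 x 5 = 15, giving 62 to 92.
- The plan speaks of 12 weeks and of assessments at weeks 5, 8 and 12. These agree with the spacing if the baseline week counts as week 1: 1 + 4 = 5, 5 + 3 = 8, 8 + 4 = 12.
- Less the two laser-day holds: 77 - 2 = 75 days (60 to 90).

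Section 9 gives one pump but no frequency, so these are days on the regimen and not a count of applications.

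**Serum days still ahead at each visit**, which is what asking the question at that visit could spare:

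- Visit 1: 75 (60 to 90).
- Visit 2: 21 + 28 - 2 holds = 47; windows +/- 10 give 37 to 57.
- Visit 3: 28 - 1 hold = 27; window +/- 5 gives 22 to 32.

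**Exposure after conception.** If the next dipstick detects the pregnancy, exposure lasts at most one visit interval:

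- Visit 1 to 2: 28 +/- 5 = 23 to 33 days.
- Visit 2 to 3: 21 +/- 5 = 16 to 26 days.
- Visit 3 to 4: 28 +/- 5 = 23 to 33 days; topical use ends at Visit 4 in any case.

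The range of these limits is 16 to 33 days. If a pregnancy is missed at one visit and found at the next, the limit becomes two intervals: 28 + 21 = 49, or 21 + 28 = 49, each +/- 10, so 39 to 59 days.

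**Number affected.** The documents give no figure for how many eligible women are breastfeeding or planning pregnancy, so no expected count can be worked out.

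**The case against.** The best case for the plan is that Section 14 is a risk disclosure and not a contraindication. Unestablished safety means absent data. The protocol describes a cosmetic with no drug ingredient, and Section 34 says no topical is investigational. For such a product a sponsor may choose to disclose and counsel, and a stated reason for inclusion would also answer the mismatch. This stands in part. A reader might infer that the plan breaches a prohibition of its own; the text does not support that, because nothing in it says these women must not use the serum. What remains is that two named groups are admitted without a rule or a reason. Having no known effect on the fetus also says nothing about breastfeeding.

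A second objection is that planned pregnancy is already handled by repeated dipsticks, removal and the obstetrician sentence. The first two do limit exposure, so it would be wrong to treat the two groups as equally unprotected. They act only after conception, however, and the obstetrician sentence excludes and removes no one.

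Third, the consent form, screening questionnaires, data collection form and product brochure are not available to this review, and a warning or question may appear there. That would make the practical risk smaller. It would not be an eligibility rule: Section 4 ties the questionnaires to the written criteria, and no written criterion acts on either answer.

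Finally, one might think that the Section 23 sentence confining personal questions to skin care history would block the new questions. It does not: Section 9 already collects medical history, medications, family history and substance use.

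**Conclusion.** The gap is real and modest. A breastfeeding woman can be randomised, with probability 7 in 14, to about 11 weeks on the serum regimen (77 calendar days, 62 to 92; 75 net of laser-day holds), and no rule excludes or removes her. Planned pregnancy is the lesser part. Exposure after conception is limited to about one visit interval, 16 to 33 days, provided that the next dipstick detects the pregnancy.

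A reader might go further and infer that participants are harmed or that the trial's results are compromised. The documents support neither: they show missing safety data for a non-drug cosmetic, the number of women involved may be zero, and the primary analysis is untouched. The day counts describe length of use and do not measure risk. They assume visits within their windows and use of the serum from Visit 1. Confidence is high that the rule is missing from the protocol text, and lower about the practical consequence, given the documents not seen. The change is worth making because it is a cheap safety improvement.

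**What to change.** Add one line, *For females: is breastfeeding or planning to become pregnant during the study*, to the Section 4 exclusion list and to the exclusion list repeated in Section 13. Both need the edit, because the Section 13 list is not a full copy of Section 4: it omits the criterion on unwillingness to forgo other products and procedures.

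Ask both questions at screening, and again with the dipstick at Visits 2 and 3, where repetition serves mainly to catch a change in pregnancy plans. Existing text does the rest: Section 4 screens on each criterion, and Sections 12 and 13 remove anyone who later meets an exclusion. Section 23 needs no change.

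The cost is one line in two places and two short questions at three visits. The eligible pool becomes slightly smaller, but Section 19 reports over 100 interested patients for 14 places.
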